2.0 Background/Scientific Rationale

Acute inflammation increases CV risk [1–4] with a higher prevalence of older adults experiencing adverse CV events[3]. Aging is associated with immunosenescence[5,6], rendering older adults more susceptible to infection[7] and may contribute to the higher mortality and acute CV events following acute inflammation in the elderly[1,2,8]. Indeed, infectious disease hospitalization and the concomitant inflammatory insult leads to an 8-fold increased risk of acute coronary syndromes in older adults within 15 days after admission[9].

[figure not shown]
Increased CV risk with acute inflammation may also stem from detrimental changes in endothelial function[10–12] and arterial stiffness[13–15]. Indeed, our laboratory has shown that endothelial function during acute inflammation decreases in younger, but not in older, adults [16,17]. Moreover, acute inflammation results in concomitant increases in arterial stiffness, a predictor of CV events. These large artery impairments during acute inflammation may be further propagated down the arterial tree to the microvasculature, altering microvascular reactivity. During a severe acute inflammation model, peripheral near-infrared spectroscopy (NIRS) evaluation of microvascular reperfusion is altered earlier than other systemic variables[18]. NIRS may therefore serve as an early detector of altered peripheral perfusion during acute inflammation. As such, identifying means to restore vascular reactivity during acute inflammation to levels seen in young adults may help attenuate CV risk in older adults.

Higher cardiorespiratory fitness and habitual physical activity are protective for many aspects of CV health[19,20] and appear to also be protective during acute inflammation. Recent data suggests voluntary running is protective against acute inflammation and the concomitant microvascular dysfunction in a mouse-model of sepsis[21].

Furthermore, population-based data suggests inadequate exercise (<1.07 MET h/day) is associated with a doubling of the risk of mortality during severe

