acute inflammation (sepsis), independent of other risk factors[22]. Additionally, during acute inflammation, our group has shown moderately fit older adults 1) maintain vascular reactivity similar to that of younger adults[23], which may help protect maintenance of blood pressure and 2) do not experience increases in arterial stiffness as seen in low fit older adults.[15] These data suggest exercise has beneficial effects in clinical manifestations of inflammation and has shown potential cardioprotective effects during acute, low-grade inflammation.

Figure 1.

The protective effect of fitness in older adults is potentially due to lower oxidative stress. Aging alone increases oxidative stress which reduces nitric oxide bioavailability, impairing baseline endothelial function (Figure 1). In older adults, habitual physical activity maintains endothelial function to similar levels as young healthy adults[24,25] and increases antioxidant defense by reducing NADPH oxidase and nuclear factor- κ B (NF κ B) activity[26]. Salsalate administration inhibits NF κ B, reducing oxidative stress, and improving endothelial function[27]. Salsalate administration improves endothelial function in older, sedentary adults but not their trained counterparts or younger adults[28]. This supports the role of fitness in reducing oxidative stress with aging.

During *acute inflammation* in young adults, endothelium-independent vasodilation remains intact, indicating the change in endothelial function is likely due to reduced nitric oxide bioavailability and increased oxidative stress[11,12]. Increases in oxidative stress have been shown at 48 hours following a vaccination[10]. Additionally, ascorbic acid has partially resurrected forearm blood flow responses to acetylcholine during acute inflammation[11]. Since being physically active while aging maintains baseline levels of oxidative stress and endothelial function similar to that of young adults, changes in oxidative stress may explain the differing conduit endothelial responses between older low and high fit adults during acute inflammation. However, the mechanism of impairment has not been fully investigated. Antioxidant intake improves vascular function in older adults to similar levels of young adults, suggesting a role of oxidative stress[29,30]. Thus, ingestion of an antioxidant such as ascorbic acid may eliminate vascular dysfunction during acute inflammation.

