A blood sample will be collected at baseline during each visit (3 times) and following Vit C consumption (2 times). During the first visit, each blood sample will be 15 mL (approximately 1 tbsp). On visit 2 and 3, the baseline blood draw will be 25 mL (approximately 5 tsp). The final blood draw on visit 3 will be 15 mL (approximately 1 tbsp). At all time points, we will measure C-reactive protein and interleukin-6 for inflammatory markers, oxidized LDL as a marker of oxidative stress, total antioxidant capacity and ascorbate for antioxidant capacity, and endothelial extracellular vesicles, in which additional analyses on inflammatory markers may be performed. The baseline blood draw of visit 2 and 3 will also assess the cholesterol panel (Total cholesterol, HDL cholesterol, non-HDL cholesterol, triglycerides, LDL cholesterol, TC/HDL ratio) and glucose. The additional 10 mL during the baseline blood draw on visit 2 and 3 will be used for analyses of peripheral blood mononuclear cells, which provide valuable information about immune function. Immediately after acquisition of venous blood, plasma or serum will be separated by centrifugation (3000g at 4°C for 15 minutes), placed in aliquots, and stored at -80°C.

Blood pressure

Blood pressure will be measured in the arm using an automated microprocessor controlled ambulatory blood pressure monitor (Mobil-O-Graph 24 PWA, I.E.M, Stolberg Germany) in the supine position according to the guidelines of the American Heart Association. BP will be measured twice, one minute apart, and the average of the two values will use as resting BP. If the two BP measurements

differ by more than 5 mmHg, a third measurement will be taken. Cardiovascular variables such as derived ascending aortic BP waveform and central arterial indices (PWV and pulse wave analysis), stroke volume and cardiac output can be calculated from the pressure waveforms.

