9.0 Data Analysis

Statistical data analysis will be conducted using IBM SPSS statistical analysis software. This study is a hypothesis generating study, designed to test the anticipated relationship of fitness with aging on vascular function and oxidative stress during an acute bout of inflammation, in generally healthy individuals. This study will provide preliminary data to conduct power analyses for future studies.

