12.0 Statistical Considerations

The data will initially be examined for normality violations, entry errors, and missing values. Entry errors will be corrected by double-checking with original data files. Non-normally distributed data will have an appropriate transformation applied to achieve normality (i.e. log transformation, square root, etc.).

All analyses will be adjusted for age, sex, and body mass index, which are all factors known to influence hemodynamic parameters. Additionally, due to multiple tests, a correction will be applied for multiple comparisons (α divided by the number of tests). Significance level will be set at $\alpha=0.05$, with a Bonferroni correction used to correct for multiple comparisons.

Aim 1: The effects of acute inflammation on endothelial and microvascular function will be tested with a two-way group (3) by time (2) repeated measures ANOVA (V2 and V3 baseline). We expect older high fit adults to have similar vascular reactivity as young adults, i.e. decreased FMD and NIRS reperfusion, suggesting that fitness maintains vascular reactivity during an inflammatory insult with age. If no difference in the response to acute inflammation is seen between low and high fit older adults (not expected), this would indicate fitness is not protective with age during acute inflammation.

Aim 2: The effects of ascorbic acid ingestion will be tested with a two-way group (3) by time (2) repeated measures ANOVA to determine if the antioxidant caused changes at Visit 1 (baseline) or Visit 3 (acute inflammation). A two-way group (3) and time (3) repeated measures (V2 baseline, V3 before and after Vit C) ANOVA will determine if the antioxidant attenuated endothelial function during acute inflammation. At baseline, we expect ascorbic acid to improve vascular function, i.e. increase FMD and NIRS reperfusion, in older low fit adults, with no changes seen in young or high fit older adults. During acute inflammation, we expect ascorbic acid to restore vascular function to baseline in young and older high fit adults. If ascorbic acid does not alter vascular function during acute inflammation, this would indicate another mechanism other than oxidative stress is contributing to vascular dysfunction.

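### Section 12.0 reads null vascular results as evidence about fitness or mechanism without first requiring that the vaccine raised inflammation or that ascorbic acid raised plasma ascorbate

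*Combined protocol and SAP*

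**What the plan says.** **Null readings.** Under Aim 1, Section 12.0 says that if low-fit and high-fit older adults show no difference in response, "this would indicate fitness is not protective with age during acute inflammation". Under Aim 2 it says: "If ascorbic acid does not alter vascular function during acute inflammation, this would indicate another mechanism other than oxidative stress". That sentence ends by attributing the vascular dysfunction to the other mechanism, so it takes dysfunction as given. No condition is attached to either statement.

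**Models.** For the first aim, "The effects of acute inflammation on endothelial and microvascular function will be tested with a two-way group (3) by time (2) repeated measures ANOVA", comparing the Visit 2 and Visit 3 baselines. Aim 2 has a two-time-point model whose outcome is not named and a three-time-point model for endothelial function. The expected results are given for FMD and NIRS only.

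**Data.** Section 6.0 (Venous blood samples) says that at every time point "we will measure C-reactive protein and interleukin-6 for inflammatory markers", with oxidized LDL, total antioxidant capacity and ascorbate. There are three baseline draws and two post-dose draws, so five in all. Section 9.0 says the study is to test the relation of fitness and aging to "vascular function and oxidative stress during an acute bout of inflammation". No section names a test for CRP, IL-6 or ascorbate.

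**The concern.** Each null reading is the last link in a chain. The Aim 1 reading assumes that the vaccine produced an inflammatory stimulus in the older participants. If it did not, neither older group would change and they would look alike whatever fitness does. The Aim 2 reading assumes that vascular function fell after the vaccine, so that there was something to restore, and that the oral dose raised plasma ascorbate. If either step failed, no ascorbic acid effect would be seen whatever the role of oxidative stress.

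Followed as written, the plan turns a failed stimulus or failed uptake into a stated conclusion about fitness or mechanism. The assays that could tell these cases apart are already planned, so the gap lies in the analysis and the inference rule, not in data collection.

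**Working it through.** The documents give no effect size, power or sample-size derivation, so there is no planned figure to reproduce. The check has three parts.

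**1. What each null needs, against what Section 12.0 tests**

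| Step | Aim 1 null | Aim 2 null | Measured | Role in Section 12.0 |
|---|---|---|---|---|
| Vaccine raised inflammation by Visit 3 | needed | acts through the next row | CRP, IL-6 | no test named |
| Vascular function fell, Visit 2 to Visit 3 pre-dose | this is the outcome | needed | FMD, NIRS | modelled, but not a condition for the null reading |
| Ascorbate rose after dosing | irrelevant (both time points precede the Visit 3 dose) | needed | ascorbate | no test named |

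The second row is not a formality. Section 12.0 expects NIRS reperfusion to fall in young adults, but the pilot in Section 2.0 (n = 16 young adults) found a reperfusion slope of 1.84 ± 0.52 before and 1.83 ± 0.49 %/s at 24 h. The pre-post correlation is not given. If it lies between 0 and 0.8, the SD of change is 0.714 to 0.321, and the 95% half-width (2.131 × SD / √16) is 0.38 to 0.17 %/s. The pilot does not exclude a fall, but it does not show one.

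**2. How often a false Aim 1 null would occur (illustration)**

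Inputs: 15 per group (Section 6.0) and alpha 0.05 (Section 12.0; two-sided is assumed). Let d be the true high-fit versus low-fit difference in vascular change, in SD of change, at full stimulus. Let f be the fraction of it elicited. Both are assumptions, as is the proportional scaling. For an unadjusted two-sample t test:

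- df = 28, critical t = 2.048
- noncentrality = f × d × √(15/2) = 2.739 × f × d
- chance of a null = P(|T| ≤ 2.048)

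| d | f = 1 | 0.75 | 0.5 | 0.25 | 0 |
|---|---|---|---|---|---|
| 0.8 | 43.8% | 64.5% | 81.5% | 91.7% | 95.0% |
| 1.0 | 24.7% | 49.1% | 73.8% | 89.9% | 95.0% |
| 1.2 | 11.3% | 33.7% | 64.5% | 87.5% | 95.0% |

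The f = 1 column shows that low power alone makes the null unsafe. Bonferroni worsens this, and its divisor is not stated. For d = 1.0 at full stimulus, power is 75% at 0.05, 58% at 0.05/3 and 47% at 0.05/6 (assumed divisors).

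**3. What marker checks can show with 15 per group**

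- Within one group, the 95% half-width for a mean change is 2.145 / √15 = 0.55 SD. The smallest change detectable with 80% power is 0.78 SD.
- Between two groups, the 95% half-width for a difference in change is 2.048 × √(2/15) = 0.75 SD. The smallest detectable difference is 1.06 SD.

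A check can therefore show that a marker moved within a group if the movement is fairly large. It cannot show that it moved equally across groups unless a margin of about 0.75 SD or more were accepted.

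**The case against.** **The study calls itself hypothesis generating (Section 9.0), and the null statements are brief remarks.** This stands as a limit on severity. It does not justify the unconditional wording.

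**Oxidative markers may already be covered.** The two-time-point Aim 2 model names no outcome. Section 6.0 repeats the oxidative-stress markers after dosing to see what the antioxidant did, and Section 9.0 says oxidative stress is tested. A reader might infer that Section 12.0 analyses vascular outcomes only, but the text does not establish that. Even on the generous reading, CRP and IL-6 have no stated test and the null readings remain unconditional.

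**The stimulus is supported by cited work.** Section 6.0 cites a rise in hsCRP to at least 32 h after typhoid vaccination, which covers the 24 h visit. Section 2.0 cites partial restoration of blood-flow responses by ascorbic acid during acute inflammation. Visit 1 uses the same dose and wait, which gives a partial functional check. All this makes the steps plausible. It does not verify them in these three groups, and no response by age or fitness group is given.

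**Two background statements invite more than they say.** A reader might take "Aging is associated with immunosenescence" to mean that low-fit older adults mount a weaker response than high-fit older adults. The statement concerns age, and both older groups are 55 to 75. A reader might also take "Increases in oxidative stress have been shown at 48 hours following a vaccination" to mean that no oxidative rise would be present at 24 h. It reports a rise at 48 h, and the cited title concerns influenza vaccination. It says nothing about absence at 24 h.

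**Conclusion.** The concern holds in a limited form: the two null conclusions are unconditional, and no test is named for whether inflammation or ascorbate rose. It should be corrected, but it is not fatal to an exploratory study. The size depends on assumptions the documents do not supply. For true differences of 0.8 to 1.2 SD, halving the elicited effect raises the chance of a null from 11–44% to 65–82%. This rests on vascular change scaling with the stimulus and on an unadjusted t test.

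Two stronger readings are not supported. First, a reader might infer that the inflammatory response must be equal across groups before any conclusion is drawn. Section 1.0 lists inflammation among the things fitness affects, so a difference in response may be part of the fitness effect, and equality cannot be shown at this sample size. For the same reason, and because no marker response by fitness group is given, the documents do not show that an observed fitness difference would be an artefact of unequal stimulus. Second, a reader might infer that the Aim 2 null is void unless oxidized LDL rose. If vascular function fell and oxidized LDL did not rise, that would itself fit another mechanism.

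The checks do not cure low power, which is a separate reason to soften both statements.

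**What to change.** Add to Section 12.0 five models, labelled as manipulation checks and kept outside the Bonferroni family:

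- log CRP, log IL-6 and oxidized LDL, Visit 2 versus Visit 3 pre-dose, by group;
- ascorbate, before versus after the dose, by group, at Visit 1 and at Visit 3.

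Report within-group changes and between-group differences with 95% CIs. A marker can be said to have risen in a group when the CI for its mean change lies above zero. With the either-or rule below and no true rise, the chance of passing in a given group is at most 2 × 2.5% = 5%.

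Then replace the two null statements with conditional ones:

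- **Aim 1:** conclude that fitness was not shown to be protective only if CRP or IL-6 rose within the older groups, and report the CI for the high-fit versus low-fit contrast in vascular change alongside.
- **Aim 2:** conclude that another mechanism is indicated only if, for the group and outcome concerned, vascular function fell from Visit 2 to Visit 3 pre-dose and ascorbate rose after dosing.
- Otherwise report the result as inconclusive.

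Do not require equal inflammatory responses across groups. Report the oxidized LDL change as an aid to interpretation, not as a condition.

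The cost is new wording and five models on assays already planned, with no new visits or samples. More results may have to be reported as inconclusive, since a within-group rise below about 0.78 SD will often be missed.

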13.0 Regulatory Requirements

13.1 Informed Consent

Oral consent will be obtained by phone or email during the screening process. All subjects will receive an informed consent document to read and sign upon arrival to the IPL during the first visit. The informed consent will describe the protocol of the study, the intended risks, and the intended benefits of study participation. After reviewing the information in the informed consent, individuals may decline to participate. For those who are willing to participate in the study, they will sign the informed consent document and continue with the visit. The original signed informed

consent document will be stored in a locked cabinet that will be accessible to IPL members and a copy will be provided to the subject.

13.2 Subject Confidentiality

Subject identity will be numerically coded. All data recorded for that subject will be labeled and stored under that numeric code. All computers used to record data are password protected.

13.3 Unanticipated Problems

When an unanticipated problem is identified, the staff member identifying the adverse event will immediately report it to the principal investigator. The principal investigator will then contact the participant and an Adverse Event Report Form will be completed. If the principal investigator feels that a serious adverse event has occurred, a report of the serious adverse event will be forwarded to the UIC IRB within 24-48 hours of occurrence. If the event is not classified as a serious adverse event, it will be reported to the UIC IRB upon the next renewal.

